3.3.2.11. Yoga Intervention: The Iyengar method uses props such that the postures can be modified to meet the physical abilities of the subjects. The yoga manual developed in Study 2 and 4 emphasizes backbends and chest opening postures consistent with the recommendations of Iyengar method for depression.(76) All yoga classes in the proposed intervention will be conducted according to the manual. Each class follows the progression of seated/reclining poses, Sun Salutation standing poses, spinal twists, back bends, forward bends and inversions and a deep relaxation (savasana). Consistent with their training, the yoga instructors are allowed to adjust poses and sequences to meet the needs of the subjects. The 90-minute yoga sessions include approximately 60-minutes of yoga postures, 10-minutes of transition and deep relaxation and a 20-minute CD of paced coherent breathing practice at a rate of 5 breaths per minute. In the Iyengar method, breathing practices start with exercises that use equal periods of inhalation and exhalation.(77) Coherence breathing uses 4 to 6 soft breathes per minute with equal periods of inhalation and exhalation consistent with the Iyengar method. This proposed study uses coherence breathing at 5 breaths per minute, an optimal rate for most people and a method successfully piloted in Study 4. Subjects will be instructed to attend 2 classes per week for a total of 24 classes. Missed classes can be made up as long as the total dose of 24 classes is not exceeded. Homework sessions for the yoga group are 15-minutes of yoga postures and 15-minutes of coherent breathing. Subjects will be provided with a yoga mat, 2 yoga blocks, 1 yoga belt, and three yoga blankets and a manual of the yoga sequences, and a CD of the paced breathing for at home practice. Additional props maybe provided for use during the virtual intervention as determined by the yoga instructors. The B.K.S. Iyengar Yoga National Association of the United States (IYNAUS) Certification Committee certifies teachers, in the B.K.S. Iyengar method for the practice and teaching of yoga. [name], head yoga teacher for Study 2 and 4, will recruit and manage the teaching schedule

for certified yoga instructors with Iyengar training who have at least 5 years teaching experience. Instruction in coherent breathing is necessary because the positive effects on sympatho-vagal balance depend not only on the respiratory rate, but also on degree of effort, depth, and muscle relaxation while breathing. Without proper instruction, some inhale too rapidly, overfill their lungs, exhale too forcefully, overuse abdominal muscles, or breathe paradoxically (contracting abdominal muscles while inhaling). Any of these errors could increase sympathetic activation, interfere with parasympathetic activation or even cause hyperventilation. (16) Instructors are needed to observe subject breathing and to monitor and provide corrective feedback.

The COVID-19 pandemic has resulted in all of the yoga instructors providing yoga classes virtually. In order to support social distancing the yoga interventions will be provided virtually through a platform approved by the ISSO officer, such as VA Video Connect. The yoga instructors will teach all yoga interventions virtually. The subjects will be required to attend the randomization, and weeks 4, 8, and 12 interventions at the VABHCS so that equipment can be provided or collect and pre and post intervention data can be collected.

3.3.2.12. Walking Intervention: The walking intervention was developed and used in Study 2. The literature documents the benefit of physical activity in the treatment of depression, such that a walking group can be considered an active control.(47) For the in-person walking intervention, subjects walk in an indoor circuit with a defined length such that the number of circuits required for a rate of 2.5 miles an hour rate are completed in 60- minutes. Subjects are monitored so that they complete 25% of the required circuits every 15-minutes. The time for the group walking intervention is 60-minutes per group session and the homework is for 15-minutes three times a week, beyond typical walking. The walking group and homework are designed to match the physical activity of the yoga group (i.e., time spent doing yoga postures), not the length of yoga sessions, this results in the walking intervention taking less time than that of the yoga group, with the extra time in the yoga group due to the breathing exercise that does not include group interactions or physical exertion. Study staff will be trained to monitor the intervention and direct subjects to ensure the correct number of laps are completed.

In order for the interventions to be as balanced as possible, the subjects assigned to the interventions will need to come to the VABHCS the same number of times as the subject assigned to the yoga intervention. For the virtual walking sessions, subjects will check in with research staff at the beginning and end of each session by video or telephone. Virtual walking sessions will also include walking at 2.5 miles an hour on a flat surface. During the screening process, subjects will be evaluated for stride length,such that the number of steps to equal 2.5 miles will be calculated. At the randomization session, subjects will be instructed on how to use the pedometer. Subjects will wear a pedometer for each walking session, both in-person and at home, the number of steps for each session will be recorded four times during the intervention and at the end of the homework to document the distance walked. Subjects can provide documentation of the number of steps by photographing the pedometer and sending an email or text or by reporting to the walking intervention monitor during the session.

3.3.2.12.1. Yoga and Walking Fidelity Assessment and Schedules: The Yoga and Walking Fidelity Assessments have 10 components that will be monitored for fidelity to the protocol. Each yoga instructor, and each walking intervention monitor will have an assessment for each quarter of study participation. An evaluation that has less than 100% fidelity to these 10 components will trigger a review of the evaluation, and a follow up evaluation will be completed within four weeks. The fidelity assessment can be used for in-person and virtual interventions. Four group sessions will be offered each week for the yoga and the walking intervention. The yoga and walking groups will be held at the same time to prevent blinded staff from deducing group assignment based on the time of the assessments. The PI may change the intervention schedule or number of session to meet recruitment and retention needs.

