A Randomized Control Trial Treating Depression With Yoga and Coherent Breathing Versus Walking in Veterans

NCT03489122

Document Date: 3-07-2022

HUMAN SUBJECTS RESEARCH PROTOCOL

Project Title: A Randomized Controlled Trial Treating Depression with Yoga and Coherent Breathing Versus Walking in Veterans

Short Title: RCT Treating Depression with Yoga or Walking in Veterans

Protocol Version and Date: Version 5 December 31, 2021

Principal Investigator (PI): [name].

Co-Investigators: [name]., Principal Investigator for the McLean Hospital.

Institution(s): The VA Bedford Healthcare System (VABHCS) is the coordinating site. The McLean Hospital, Belmont MA will be the site for MRI imaging.

1.0 OBJECTIVE AND SPECIFIC AIMS:

Aim 1: To determine in Veterans, the effectiveness of an RCT of 12-weeks of the yoga intervention versus walking intervention, with depression and mood assessed at baseline prior to randomization, and prior to and immediately following yoga or walking interventions at weeks 4, 8, and 12, and before each scan.

Hypothesis I: In this working clinical hypothesis, subjects in the yoga group will exhibit greater improvements in depressive symptoms and mood ratings over the study compared to the walking group.

Aim 2: To measure changes in thalamic GABA levels at Scans 1, 2, and 3. (3)

Hypothesis II: In this working translational hypothesis, GABA levels will increase and depressive symptoms will decrease over the course of the 12-week intervention in the yoga group compared to the walking group.

Aim 3: To examine changes in RSA acquired at baseline prior to randomization, and prior to and immediately following yoga or walking interventions at weeks 4, 8, and 12, and before each scan.

Hypothesis III: In this working translational hypothesis, RSA levels will increase and depressive symptoms will decrease over the course of the 12-week intervention in the yoga group compared to the walking group.

Exploratory Aim: If an individual has symptoms of Post Traumatic Stress Disorder (PTSD) at screening, there will be a greater decline in PTSD symptoms with treatment in the yoga compared to the walking group. The use of the 3T scanner allows the collection of pre and post exploratory data for cortical thickness, resting state, and executive function.

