2.2.d. Changes in Mood Scores: Study 2 utilized the Spielberg State Trait Anxiety Inventory (STAI), State and Trait subscales, and the Exercise Induced Feeling Inventory (EIFI) with subscales for Revitalization, Tranquility, Revitalization, and Physical Exhaustion.(56, 57) These scales were selected because they can be given repeatedly to measure current mood states over time. Mood assessments were obtained at baseline, before each scan, and at weeks 4, 8, and 12. Groups did not differ on demographic variables or STAI Trait anxiety scores. Tonic changes over the course of the study (Scan 2 – Scan 1) for mean mood scores showed significant increases in the yoga group for Revitalization (1.8 ± 2.5 , $t_{18} = 3.21$, $p = 0.005$). Acute changes from pre- to post-intervention (Scan 3 – Scan 2) for mean mood scores showed significant increases in the yoga group for Revitalization (2.5 ± 2.7 , $t_{18} = 4.12$, $p < 0.001$) and Tranquility scores (2.0 ± 1.8 , $t_{18} = 4.77$, $p < 0.001$), and a significant decrease in STAI-State anxiety scores, consistent with decreased anxiety (-5.2 ± 5.5 , $t_{17} = -4.05$, $p < 0.001$). A Generalized Estimating Equation (GEE) analysis of mean mood scales at baseline, and weeks 4, 8, and 12, showed the yoga group to have significantly greater improvement than the walking group on all subscales of the EIFI, with significant increases in Tranquility, Revitalization and Positive Engagement, and significant decreases in Physical Exhaustion.

2.2.e. Study 3 (9), Streeter et al 2012⁹: This study compared GABA/Cr in subjects with MDD who were enrolled in a 12-week trial of Hatha yoga for low back pain (Saper 2009) and with healthy controls from Study 2.(58) Iyengar yoga is a subset of Hatha yoga. The Iyengar yoga 12-week intervention from Study 2 and the Hatha yoga 12-week intervention for Low Back Pain were reviewed by a certified Iyengar instructor and found comparable. The MRS protocols used to collect GABA/Cr were identical in both studies. This allowed Scan 1, obtained before the 12 week interventions and Scan 2 after the interventions to be compared in healthy controls ($n=19$) from Study 2 and subjects with MDD and low back pain from Study 3 ($n=2$). At baseline, the MDD subjects with low back pain demonstrated lower GABA/Cr, which increased over the course of the 12-week yoga intervention, as depressive symptoms and low back pain declined.

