3.0 RESEARCH DESIGN AND METHODS

3.1 Drug/Device Information: NOT APPLICABLE

3.2 Type of Study: (Table 3: Individual Timeline): This is a longitudinal, efficacy randomized controlled trial (RCT). Veterans with MDD will be evaluated for eligibility and randomized to a 12-week intervention of a twice-weekly yoga and coherent breathing or walking group. As there is evidence that exercise improves mood in unipolar depression, the walking group will serve as an active control condition.(47) The policy for Common Data Elements will be incorporated into the data collection matrix. The Consolidated Standard of Reporting Trials (CONSORT) will be used to ensure the quality of reporting for this RCT.(48) The **primary dependent variable** will be changes in the Hamilton Depression Rating Scale (covering a 2 week period), and mood and anxiety scales (designed for repeated use, such that changes from pre to post intervention can be gauged), measured using valid and reliable psychological instruments obtained at screening, intervention weeks 4, 8, and 12, and before each MRS scan. The **secondary dependent variable** will be brain gamma amino-butyric acid (GABA) levels measured by magnetic resonance spectroscopy (MRS) in the left thalamus, the same region used in our prior studies.(9, 53, 65) The thalamus has the technical advantage of providing high quality spectra, has a high concentration of GABAergic neurons, and thus a high GABA signal, in which changes can be detected. The thalamus is also anatomically connected to other regions of interest. GABA levels will be measured by MRS in 3 separate scan acquisitions: before randomization (Scan 1), after 12-weeks of the yoga or walking intervention (Scan 2), followed immediately by the group assigned intervention and the final scan (Scan 3). The **third dependent variable** will be respiratory sinus arrhythmia (RSA) a component of heart rate variability (HRV) that is an accurate index of vagal influences on the heart.RSA will be measured before each scan and before and after an intervention at week 4, week 8 and week 12. Medications also are evaluated at weeks 4, 8, and 12. Two and six month follow-up phone calls will assess depression, quantity of yoga practice, and barriers to practice.

3.3.1. Sub-Study Participation: This is not a multisite study. There will be a contract with the McLean Hospital for goods and services regarding the imaging component of this study.

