- (10) **Pittsburgh Sleep Quality Index (PSQI)** is a self-administered instrument that assesses 9 factors of sleep over a month period, providing a composite score, with higher scores indicating poorer sleep quality.(71)
- (11) **Timeline Follow Back (TLFB)** will be used to assess alcohol consumption for three months prior to screening.(72) A format similar to the TLFB will be used for nicotine consumption.
- (12) **Brief Pain Inventory**, an eleven point Likert Scale of pain intensity will be used to assess pain over the last 24 hours.
- (13) **Stroop Color-Word Test** is a selective attention and inhibitory cognitive control task.(74)

Individual Time Line	Table 3: Individual Time Line and Collection of Dependent Variables		
	Aim 1	Aim2	Aim 3
Individual Time Line	Depression Scales	Mood Scales	GABA RSA
Telephone Screen			
Screening Session	HDRS/BDI-II 1		
3T Brain Scan			
MRS Imaging Session 1			
Pre Scan 1 Measures	HDRS/BDI-II 2	EIFI & STAI 1	RSA 1
MRS Scan 1(Baseline)			GABA 1
Randomization			
Week 4			
Pre-Week 4 Evaluation		EIFI & STAI 2	RSA 2
Week 4 Intervention			
Post-Week 4 Evaluation	HDRS/BDI-II 3	EIFI & STAI 3	RSA 3
Week 5-7 Intervention			
Week 8			
Pre-Week 8 Evaluation		EIFI & STAI 4	RSA 4
Week 8 Intervention			
Post-Week 8 Evaluation	HDRS/BDI-II 4	EIFI & STAI 5	RSA 5
Week9-11 Intervention			
Week 12			
Pre-Week 12 Evaluation		EIFI & STAI 6	RSA 6
Week 12 Intervention			
Post-Week 12 Evaluation	HDRS/BDI-II 5	EIFI & STAI 7	RSA 7
MRS Imaging Session 2			
Pre Scan 2 Evaluation	HDRS/BDI-II 6	EIFI & STAI 8	RSA 8
Scan 2			GABA 2
Interscan Intervention			
Pre-Scan 3 Evaluation		EIFI & STAI 9	RSA 9
Scan 3			GABA 3
Follow-Up 2 month	HDRS/BDI-II 6	EIFI & STAI 10	
Follow-Up 6 month	HDRS/BDI-II 6	EIFI & STAI 11	

(14) **Digit Symbol Substitution Test (DSST)** is one of the frequently used tests to measure psychomotor slowing, and is clinically sensitive because it makes demands on several processes, including perception, working memory, sustained attention and visuomotor co-ordination (Wechsler 1997).

(15) **Child Trauma Questionnaire (CTQ)** is a self-report measure of childhood trauma. (73) This scale will be given during the Week 4 evaluation at the end of the session.

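### On-treatment HDRS and BDI-II are scheduled only after that day's session, so the depression comparison can absorb any yoga-minus-walking difference in acute session effect

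*Protocol*

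**What the plan says.** Protocol Table 3 lists, for weeks 4, 8 and 12, a pre-session evaluation and a post-session evaluation. EIFI, STAI and RSA appear in both. HDRS and BDI-II appear only in the second: "Post-Week 4 Evaluation HDRS/BDI-II 3", "Post-Week 8 Evaluation HDRS/BDI-II 4" and "Post-Week 12 Evaluation HDRS/BDI-II 5". The two baseline ratings, at screening and at "Pre Scan 1 Measures HDRS/BDI-II 2", come before randomization and follow no session. One end-of-treatment rating is not tied to a session: "Pre Scan 2 Evaluation HDRS/BDI-II 6", which comes before the interscan session.

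Other sections describe the schedule differently:

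- Aim 1 (Protocol 1.0) has depression and mood assessed at baseline, then "prior to and immediately following yoga or walking interventions at weeks 4, 8, and 12", and before each scan.
- Protocol 3.2 includes a time before each MRS scan among the collection times for the HDRS and the mood scales.
- The text after the instrument list in 3.3.2.1 adds pre- and post-session administration for EIFI and STAI-State only. For the two imaging sessions it lists instruments 2, 5, 13 and 14, which includes the BDI-II (5) but not the HDRS (4).

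The analysis text (Protocol 3.5.1, SAP D.17) names four time points, pre-randomization and weeks 4, 8 and 12, and tests the group-by-time interaction. It does not mention the pre-Scan 2 rating.

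**The concern.** Hypothesis I is about improvement over the course of the study. If Table 3 governs, every on-treatment depression value in the model is taken after a session and the baseline is not. A short-lived lift from that day's session would then count as change since baseline.

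The sessions differ by arm. Yoga takes 90 minutes and includes deep relaxation and 20 minutes of paced breathing (3.3.2.11); walking takes 60 minutes (3.3.2.12). The acute lift may therefore differ by arm too. The plan separates acute from lasting change for mood and RSA by measuring both before and after the session, but it cannot do so for its depression scales at weeks 4, 8 and 12. Blinding the rater does not help with this, because the effect would lie in what the subject reports.

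There is also a blinding question. Section 3.3.2.12.1 runs the two groups at the same time so that blinded staff cannot infer the arm from the time of assessment. With sessions of 90 and 60 minutes, that protects a pre-session rating better than a post-session one.

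**Working it through.** **1. Timing of each depression rating (Table 3) and its use in the model (Protocol 3.5.1, SAP D.17).**

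| Rating | Follows a session? | Named in the model? |
|---|---|---|
| Screening; pre-Scan 1 | No | Yes, as pre-randomization (which of the two is not stated) |
| Weeks 4, 8 and 12 | Yes, all three | Yes |
| Pre-Scan 2 | No | No |

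On Table 3, all on-treatment values in the interaction test are post-session and all baseline values are not.

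**2. What can enter each contrast.** Let A_y and A_w be the acute session effects on the depression score in the yoga and walking arms.

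- Between arms, week 12 minus baseline: lasting difference + (A_y − A_w). Both arms are rated after their own session, so only the difference matters.
- Within yoga (Hypothesis 1a): lasting change + A_y. Nothing offsets it.

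**3. What the documents say about the size of A.** Section 2.2.d reports acute changes in the Study 2 yoga group (Scan 3 minus Scan 2), including "a significant decrease in STAI-State anxiety scores, consistent with decreased anxiety". Checking t = mean / (SD/√n):

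- STAI-State: 5.2 / (5.5/√18) = 4.01 in absolute value (stated 4.05); 5.2/5.5 = 0.95 SD of change.
- Revitalization: 2.5 / (2.7/√19) = 4.04 (stated 4.12); 2.5/2.7 = 0.93.
- Tranquility: 2.0 / (1.8/√19) = 4.84 (stated 4.77); 2.0/1.8 = 1.11.

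These agree with the stated values within rounding. They are momentary scales in subjects without Axis 1 disorders, and no acute walking change is reported. The documents give neither A_y nor A_w for HDRS or BDI-II.

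**4. Illustration in SD units.** Assumptions: no lasting difference, 35 completers per arm (3.5.2), a simple two-sample t-test at week 12 with 68 df, two-sided 0.05 (critical value 1.995). The noncentrality is d × √(35/2) = 4.183d.

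| Assumed A_y − A_w in favour of yoga | Noncentrality | Chance of a significant result favouring yoga |
|---|---|---|
| 0 | 0 | 2.5% |
| 0.1 SD | 0.418 | 6.1% |
| 0.2 SD | 0.837 | 12.8% |
| 0.3 SD | 1.255 | 23.5% |

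**5. The same in BDI-II points.** Taking the SD of change as 9.3 (Study 4 low-dose group, 2.2.h) in both arms, SE = 9.3 × √(2/35) = 2.22. By the normal approximation, arm differences of 0, 1, 2, 3, 4 and 5 points give two-sided rejection rates of 5%, 7%, 15%, 27%, 44% and 61%.

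**6. Rating time.** If both groups start together, post-session evaluations begin 90 − 60 = 30 minutes apart by arm.

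**The case against.** A reader might infer that the 12-week result is shown to be inflated by the acute effect of yoga. The documents do not support that, for four reasons.

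- No acute change in HDRS or BDI-II is reported anywhere. Section 3.2 describes the HDRS as "covering a 2 week period), and mood and anxiety scales (designed for repeated use, such that changes from pre to post intervention can be gauged", which sets a two-week depression rating apart from scales meant to register session effects. Rating depression once per visit looks deliberate.
- The Study 2 figures are within-yoga changes on state scales in healthy subjects. Walking is an active control and may lift mood as well, so the arm difference could be near zero.
- The 0.95 SD change in STAI-State is scaled to its own change SD and says nothing about how much carries over to HDRS. The rejection rates rest wholly on assumed shifts, in a simple week-12 test rather than the planned mixed model.
- The order of assessments within the post-session visit is not stated, so the gap between session and rating is unknown.

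All of this stands. It limits the claim to a possible bias of unknown size. A two-week recall window dampens carry-over but does not exclude it.

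The pre-Scan 2 rating is a real safeguard in the schedule. As written, though, no analysis uses it, and the instrument text leaves the HDRS out of the imaging sessions. Nor does Aim 1 settle the matter. Read literally, it provides pre-session depression scores, but Table 3 does not schedule them, and the instrument text gives only EIFI and STAI-State both before and after sessions.

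Moving the full HDRS interview is not shown to be free either. Morning sessions start at 8 am, the principal investigator's tour starts at 7:30 (3.4.3.7), and clinical staffing is 50% time (5.0).

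**Conclusion.** The point holds as a design weakness and an unreconciled schedule, not as demonstrated bias. On Table 3, the group-by-time test of depression compares a baseline that follows no session with on-treatment ratings that all follow one. The between-arm contrast can absorb A_y − A_w, and Hypothesis 1a can absorb all of A_y. The plan has no depression measurement at weeks 4, 8 and 12 with which to separate either from lasting change.

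The size is not in the documents and could be zero. The 6%, 13% and 24% figures hold only under assumed arm differences of 0.1, 0.2 and 0.3 SD, no lasting benefit, and a week-12 t-test with 35 per arm.

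Two parts do not depend on any assumed effect size. Aim 1, Table 3 and the instrument text conflict on when depression is rated and on whether HDRS is collected before Scan 2. And if the groups start together, a gap of about 30 minutes in post-session rating times can reveal the arm to a blinded HDRS rater. The common start is itself an inference from the sessions being held at the same time.

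No sample-size figure changes.

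**What to change.** 1. Reconcile Aim 1, Table 3 and the instrument text in 3.3.2.1. Confirm that HDRS as well as BDI-II is collected before Scan 2, and state in 3.2 and the SAP which rating is the primary end-of-treatment value.
2. Pre-specify an analysis that uses the pre-Scan 2 rating as a check on the week-12 result: BDI-II at least, and HDRS if collected. This needs no new visit. It is informative only for subjects who attend that session, and 3.3.2.17 lets the study proceed without imaging, so report how many contribute.
3. For subjects not yet assessed, take the BDI-II at the existing pre-session evaluations at weeks 4, 8 and 12, and the HDRS there too where the visit schedule allows. Keep EIFI, STAI and RSA both before and after the session.
4. Record for every depression rating whether it was made before or after the session, and account for this in the model if both timings occur.

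The cost is a protocol and SAP amendment, a longer pre-session block, and possible scheduling strain before 8 am sessions, mainly from the clinician-administered HDRS. A change during the trial would mix pre- and post-session ratings in one dataset, which is why item 4 is needed.

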3.3.2.2. If interested they will be provided information about the study and will be allowed to proceed to the telephone interview. These techniques have been used successfully in previous VABHCS studies of yoga interventions.(59) The VABHCS Institutional Review Board (IRB) will pre- approve all forms of advertisement. Current VA policy does not allow email communications as part of the recruitment procedures. Sample size calculations, based on power analyses, require the following number of completers equally divided between the yoga and walking groups to test the hypotheses for each dependent variable: **n=70** completers to test Aim 1: Depressive Symptoms and Mood Scale; **n=56** to test Aim 2: GABA changes; and **n=68** to test Aim 3: RSA changes [D.20]. To meet the criteria for each Aim/Dependent Variable n=70 subjects will complete the intervention with n=56 having usable MRS data. Using data from Study 4, with consideration of changes in inclusion and exclusion criteria and research setting, the following recruitment schedule will be required during a 5-year study period, which will include over 4 years of recruitment and treatment. The required total recruitment and annual requirements at each stage are as follows: telephone screen=420 total or 105/year; screening interview=173 total or 43/year; randomization=100 total or 25/year; and completers=68 total or 18/year.

3.3.2.3. Participation in Non-Assigned Group: A Retention Plan: Prior to randomization, subjects will be asked their group of choice (i.e., yoga or walking), as not being assigned to a group of choice could influence dropout rate. In order to retain subjects not assigned to their choice, subjects will be allowed to participate in the group they are not assigned to for 16 sessions or 8 weeks (i.e., the second intervention), whichever comes first, if they complete their randomized intervention and 14 week follow up phone call. Retention in the randomized intervention is given priority over contamination of the 6-month follow up with the 2nd intervention. There will be no difference in how subjects in the randomized intervention or second intervention will be monitored during the first eight weeks of the intervention. Subjects will not be paid for class attendance or evaluations during the 2nd intervention nor will they undergo MRS scanning. These data are exploratory.

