Hypothesis 4. a. Exploratory Concurrent Antidepressants: The yoga group but not the walking group will have a decrease in depressive symptoms regardless of antidepressant treatment at the beginning of the study.

Hypothesis 4. b. Exploratory PTSD Symptoms: If PTSD symptoms are present at screening, there will be a greater decrease in PTSD symptoms in the yoga compared to the walking group as measured by CAPS and PCL-C.

Hypothesis 4. c. Resting State Connectivity will increase over the course of the study with greater increases in the yoga group.

Hypothesis 4. d. Executive Function will increase over the study as measured by the Stroop, Digit Symbol test and fMRI activation.

3.5.2. Power Analysis for Depressive symptoms and Mood Scales: Based on the power analyses below, in order to achieve adequate power for all analyses, n=70 subjects, n=35 in the yoga and n=35 in the walking intervention must complete the interventions. Using Study 4 data in subjects with MDD in the LDG, the repeated measures ANOVA for EIFI scores from screening to the completion of the intervention did not reach statistical significance in the group of n=15 (baseline: 3.1 ± 2.2 and week-12: 3.9 ± 2.7 , $F_{1,13} = 1.097$, $p = 0.31$), a post hoc power analysis was conducted, which determined that the achieved effect size was $f = .281$, with 52% power. Based on this same effect size, an a priori power calculation was conducted, which determined that **n=35** subjects would be needed to detect significant differences for BDI-II, STAI, and EIFI scores from screening to the completion of the intervention, with effect size $f = .281$, with $< = .02$ to account for multiple comparisons, and 81% power. As the power analysis for the EIFI requires the largest number of subjects (n=70), which will be used to determine sample size. In order for 70 subjects to complete the intervention, assuming a 20% drop out, 84 subjects will be randomized.

3.5.3. Power Analysis for GABA: Consistent with our analytic plan for the longitudinal questions at-hand, we can compute the statistical power for Hypothesis II an analysis sample of **n=26** subjects in each of the study groups using the mixed linear model analogue of repeated measures analysis-of-

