4.5.2.9. Recruitment: This proposal contains a randomized controlled trial in a clinical population in which 70 subjects will complete the protocol and around 420 will have a telephone-screening interview. Although this efficacy trial is not large or multi-centered, it is considered a Phase 2 trial due to the previous trial in healthy controls (Study 2) and the dosing trial in depressed subjects (Study4).

Sample size calculations, based on power analyses, require the following number of completers equally divided between the yoga and walking groups to test the hypotheses for each dependent variable: n=70 completers to test Aim 1: Depressive Symptoms and Mood Scale, n=56 to test Aim 2: GABA changes and n=68 to test Aim 3: RSA changes. To meet the criteria for each Aim/Dependent Variable 70 subjects will complete the intervention with 56 having usable MRS data. Using data from Study 4, with consideration of changes in inclusion and exclusion criteria and research setting, the following recruitment schedule will be required during a 5 year study period, which will include over 4 years of recruitment and treatment. The required total recruitment and annual requirements at each stage are as follows: telephone screen 420 total or 105/year; screening interview 173 total or 43/year; randomization 100 total or 25/year; and completers 70 total or 18/year over a 4 year recruitment period.

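### Randomizing 84 at 20% dropout gives 67 completers, not the 70 stated, and it conflicts with the 100 randomized in both recruitment sections

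*Protocol*

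**What the plan says.** **Completers.** Section 3.5.2 requires that "n=70 subjects, n=35 in the yoga and n=35 in the walking intervention must complete the interventions". Section 3.3.2.2 agrees in its text: "To meet the criteria for each Aim/Dependent Variable n=70 subjects will complete the intervention with n=56 having usable MRS data". The recruitment schedule that closes the same section reads "completers=68 total or 18/year". The parallel schedule in 4.5.2.9 gives 70 completers with the same 18 per year.

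**Randomized.** Section 3.5.2: "In order for 70 subjects to complete the intervention, assuming a 20% drop out, 84 subjects will be randomized". Section 4.5.2.9: "randomization 100 total or 25/year", and 3.3.2.2 has the same total of 100.

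**GABA.** Section 3.5.3 computes power for "an analysis sample of n=26 subjects in each of the study groups", which is 52 in total. Sections 3.3.2.2 and 4.5.2.9 list what the power analyses are said to require, and there the entry is "n=56 to test Aim 2: GABA changes".

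The SAP (D.17) contains no sample size, dropout rate or recruitment target.

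**The concern.** The step from completers to number randomized is the last link in the sample-size derivation, and as written it fails on its own inputs. The protocol also carries two different totals to randomize, 84 and 100, and only the first comes with a dropout rate.

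The practical stake is monitoring and reporting. Section 3.3.2.15 has recruitment goals checked every six months, and section 4.6.2.1 has the data monitoring committee follow accrual and retention. Over four years, 84 means 21 randomized per year and 100 means 25, so the same accrual could be on schedule by one section and behind by another. CONSORT reporting, which section 3.2 adopts, needs one planned number with its derivation.

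**Working it through.** **1. The 84 in section 3.5.2.** Inputs from that section: 70 completers, dropout d = 0.20.

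- The plan's figure is reproduced by 70 x (1 + 0.20) = 84.
- Number needed: N = 70/(1 - d) = 70/0.80 = 87.5, so 88. Per arm: 35/0.80 = 43.75, so 44, and 2 x 44 = 88.
- Yield of 84: 84 x 0.80 = 67.2, about 67 completers. This is 3 below the 70 for Aim 1 and also just below the 68 listed for Aim 3.
- Dropout at which 84 would suffice: 1 - 70/84 = 16.7%.

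**2. The 100 in sections 3.3.2.2 and 4.5.2.9.**

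- Implied dropout with 70 completers: 1 - 70/100 = 30%.
- At the stated 20%, 100 x 0.80 = 80 completers.
- The schedule is said to draw on Study 4, adjusted for changed criteria and setting. Section 2.2.h reports that 30 of 32 completed Study 4, a loss of 2/32 = 6%. No section states or derives 30%.

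**3. The 68 completers in the 3.3.2.2 schedule.** 70/4 = 17.5, which rounds to the 18 per year printed beside it; 68/4 = 17 does not. The 68 is also the Aim 3 requirement in the same section (2 x 34, from 3.5.4).

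**4. GABA, 52 against 56.** Inputs from section 3.5.3: yoga means 0.28, 0.285, 0.32; walking 0.28 throughout; SD 0.06; correlation 0.65 or 0.70; two-sided alpha 0.05. I used the group-by-time F test for two groups and three times under compound symmetry.

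- Group differences are 0, 0.005, 0.04, with mean 0.015. The interaction effects are half the deviations from that mean: -0.0075, -0.005, 0.0125. Their sum of squares is 0.0002375.
- Noncentrality = 2n x 0.0002375 / [0.06² x (1 - rho)], with 2 and 4(n - 1) degrees of freedom.

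| n per arm | Total | rho | Noncentrality | Power |
|---|---|---|---|---|
| 26 | 52 | 0.65 | 9.80 | 79.5% |
| 26 | 52 | 0.70 | 11.44 | 85.6% |
| 28 | 56 | 0.65 | 10.56 | 82.6% |
| 28 | 56 | 0.70 | 12.31 | 88.2% |

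With 26 per arm the plan's 80% and 85% are reproduced. So 52 is the figure in the power analysis, and 56 is not its output. 56 is exactly 80% of 70, which fits a planning allowance for unusable scans.

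**5. What three completers cost.** Section 3.5.2 sizes the trial on the EIFI (f = 0.281, alpha 0.02, 35 subjects, 81% power). It gives no within-subject correlation. Assuming two measurements and a correlation of 0.5, a one-group repeated-measures F test gives 80.6% with 35, which matches the stated 81%. With 34 it gives 79.2% and with 33 it gives 77.8%. 67 completers would leave arms of about 33 and 34, so the loss is about 1.4 to 2.9 points. The level depends on the assumed correlation (47.3% with 35 at correlation 0, 96.3% at 0.7), but the drop from 35 to 33 stays small: 2.8 points at 0, 3.2 at 0.3 and 1.2 at 0.7.

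**The case against.** The strongest reply is that little turns on this. Both recruitment sections give 100, and 84 appears once. If 100 governs, there is no shortfall at 20% dropout, because 80 would complete. The planned analysis is not limited to completers either: section 3.5.1 and the SAP specify mixed models that accept differing numbers of time points per subject and refer to an intent-to-treat analysis, so participants who drop out still contribute data. All of this stands, and it keeps the point small. It does not repair the 84 or explain the 100.

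One might suppose that 100 counts people assigned and 84 those who start. Sections 4.5.2.4 and 4.5.2.8 give a single definition of randomized, taking part in the first intervention, and no section draws that distinction. Even then, 84 at 20% would not give 70.

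Three stronger readings are tempting, and the documents do not support them:

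- *That 68 is a rival completer target.* It appears once as a total, beside an annual rate that fits 70, in a section that twice states 70. It reads as a slip.
- *That either 52 or 56 must be wrong, or that the GABA aim is short of subjects.* 52 analysed and 56 planned can both stand, and 56 exceeds 52. Only the statement that the power analysis requires 56 is incorrect.
- *That these numbers decide when recruitment ends.* No section makes any of them a stopping rule; they appear as a schedule and as targets.

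**Conclusion.** The inflation in section 3.5.2 is an arithmetic error: at the stated 20%, 88 are needed and 84 yields 67. The 84 also contradicts the 100 in sections 3.3.2.2 and 4.5.2.9, whose implied 30% dropout is neither stated nor justified. Neither the protocol nor the SAP reconciles them.

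The size is modest. The shortfall is three completers, conditional on 84 being operative and on dropout being 20%. The power cost of roughly one to three points rests on my assumed correlation and two measurements. If 100 is operative, the fault is an unsupported dropout assumption rather than a shortfall. The 68 and the 56 need wording corrections only. This is a fault of consistency and derivation that should be corrected; it does not threaten the trial's conclusions.

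**What to change.** State one expected dropout rate with its justification, derive the number randomized as 70/(1 - d), and carry that number through 3.3.2.2, 3.5.2 and 4.5.2.9. At 20% it is 88 (44 per arm). If 100 is kept, replace the 20% in 3.5.2 with the dropout that 100 is meant to allow for, at most 30%, and give the reason. The rate should be argued from retention data and the changed setting, not back-calculated from 70/100.

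Minor corrections:

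- In the 3.3.2.2 schedule, change 68 completers to 70.
- In 3.3.2.2 and 4.5.2.9, say that the GABA power analysis uses 52 (26 per arm, about 80% power at correlation 0.65), and that 56 is the planned number with usable MRS data (about 83% power at the same correlation).

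Cost: a text amendment. If 100 is the working target, no participants are added. If 84 is, the correction adds 4 participants (to 88) or 16 (to 100).
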